**Table 2: RE-AIM Outcomes for Motivate and Activate Trials**

RE-AIM Domain/Outcomes
REACH Enrollment by key subgroups for reach: income, birth country, age strata. Measurement: Screening Tool
EFFECTIVENESS (Participant level) Primary outcome in Aim 2 and 3 Trials
ADOPTION (Provider and staff level) Thematic results on barriers and facilitators of adopting intervention in other CBO settings, other populations Measurement: Endpoint Survey, Qualitative
IMPLEMENTATION (Participant, CBO-level) Fidelity: -Fidelity to CHW script (content, structure) -% participants completing receiving text -% completing CHW counseling if assigned Adaptations: Type, timing and reasons to CHW counseling or recruitment Process: Time spent on interventions, number of CHW follow-ups for navigation Satisfaction with intervention components: Participant level: Median scores for domains within patient satisfaction survey; Thematic results from IDIs and barriers and facilitators of vaccination and recommending vaccine to eligible people in social networks CHWs/Stakeholders: Perceived barriers and facilitators on adapting the intervention to other vaccines or in other settings Health system barriers and facilitators of getting RSV vaccination Measurement: CHW logs, Endpoint survey, Qualitative
MAINTENANCE (CBO-level) Barriers and facilitators of maintaining the intervention Measurement: Endpoint Survey, Qualitative

## 4. Study Design

### 4.1. Characteristics

**Study Overview.** In this type 1 hybrid-implementation study we will leverage our well-established UES collaboration, a community-academic partnership. We will uphold community-based participatory research principles throughout the study. In Aim 1, a developmental aim, we will use the ADAPT-ITT framework to adapt two intervention components, CHW counseling and text-messages nudges from a CBO, to increase RSV vaccine uptake in Latino older adults ( $\geq 50$  years) who are eligible for RSV vaccination (Aim 1a) and to activate Latino adults (18-49 years) to discuss RSV vaccination with older adults in their family and social network (Aim 1b).

We will also conduct a community-based anonymous survey to assess knowledge and perceptions about RSV and RSV vaccine knowledge. Then, in **Aim 2 (Motivate Trial)**, we will randomize 400 Latino older adults to CHW counseling *and* text message nudges vs. CHW delivered RSV vaccine information flyer at enrollment + text-message nudges, all adapted in Aim 1a. The primary outcome in Aim 2 is RSV vaccine uptake. In **Aim 3 (Activate trial)**, using a parallel design we will randomize 350 Latino adults (18-49 years) to CHW ‘activation’ counseling to encourage them to discuss RSV vaccine with people over 50 and older in their network *and* text-message nudges vs. RSV vaccine information flyer at enrollment + text-message nudges, all adapted in Aim 1b. The primary outcome for Aim 3 is average proportion of older adults in participants’ social network with whom they discussed RSV vaccination. We will incorporate implementation outcomes as secondary outcomes, which we will evaluate using the Reach, Effectiveness, Adoption, Implementation and Maintenance (RE-AIM) framework, an integrated framework to improve adoption and sustainable implementation of interventions and includes an explicit focus on equity to address dynamic implementation contexts. Our overall study design is in line with a type-1 hybrid effectiveness-implementation trial, which tests an intervention effectiveness as a primary aim, while gathering information on its delivery or implementation in the real-world. Table 3 provides an overview of the overall study design and primary outcomes.

**Table 3: Study Overview**

Aim	Study Population	Study Design and Intervention	Outcomes
1	1. Community Advisory Group: 1a. Latino adults $\geq 60$ yr 1b. Latino adults 18-50 yrs. N~35 2. Anonymous Community Vaccine Hesitancy Survey (18+ years)	1. Adaptation of intervention components using ADAPT-ITT framework. Includes in-depth interviews and formation of community advisory groups for 1a and 1b. 2. Predictors of vaccine hesitancy	Developmental Aim Products Primary : Adapted intervention components Secondary : Publication on ADAPT-IT process of adapting core-intervention components
2	400 Latino adults $\geq 50$ years, who have not received the RSV vaccine	Motivate Trial: Randomized Trial with 2 groups 1. Flyer & text-message nudge from CBO 2. Flyer & text-message nudge from CBO AND CHW counseling	Primary : RSV vaccine uptake at 60 days per CAIR Secondary : RSV vaccine uptake at 60 days per self-report; RSV vaccine uptake at 90 days per CAIR; appointment made at 60 days in clinic or pharmacy with intent to get RSV vaccine; median time to vaccination; increase in RSV vaccine confidence; increase in motivation to get RSV vaccine; increase in RSV vaccine knowledge; average proportion of social network contacts $\geq 50$ with whom participant discussed RSV vaccination at 60 days; implementation outcomes per the RE-AIM framework
3	350 adults, 18-50 with stratified sampling by age-group.	Activate Trial: Randomized Trial with 2 groups 1. Flyer & text-message nudge from CBO 2. Flyer & text-message nudge from CBO AND CHW ‘activation’ counseling	Primary : Average proportion of social network contacts $\geq 50$ with whom participant discussed RSV vaccination at 60 days (referred to as ‘Activation’) Secondary : Implementation outcomes per RE-AIM framework; increase in RSV vaccine confidence; increase in motivation to discuss the RSV vaccine with eligible family members or friends; increase in RSV vaccine knowledge; discussed RSV vaccination with $\geq 1$ $\geq 50$ -year-old at 60 days

**Qualitative Studies for Aim 2 and 3: In-depth interviews** from participants in each group including those who meet the primary outcome and those who do not  
**Focus Groups:** CHWs, key stakeholders focusing on implementation outcomes

#### 4.1.1. Study Setting

This study will take place in San Francisco at Latino Task Force (LTF)-affiliated community sites and will leverage the existing infrastructure and reach of the Unidos en Salud collaboration, a community academic partnership between the Latino Task Force and UCSF. The Latino Task

[figure not shown]
force is a coalition of over 30 Latino focused CBOs and based at the Mission Language Vocational School (MLVS), a CBO in San Francisco's Mission District.

## 4.2. Study Design for Developmental Aim 1

The overall objective of Aim 1 is to adapt the 'Motivate, Vaccinate, Activate' CHW counseling and text-message intervention to increase RSV vaccine uptake and to activate younger adults to discuss RSV vaccination with older adults in their social networks.

### 4.2.1. Overview of Aim 1 (Figure 1)

[figure not shown]
In this developmental aim, we will use the ADAPT-ITT (Figure 2) implementation science framework to adapt two core intervention components from our Motivate, Vaccinate Activate Strategy (CHW vaccine counseling and text-message nudges) to promote RSV vaccine uptake among Latino older adults ( $\geq 50$  years).

( $\geq 50$  years) (**Aim 1.1**) and activate adults (18-49 years old) to discuss RSV vaccination with older adults in their social and family networks (**Aim 1.2**). In Figure 2 we outline the ADAPT-ITT process. As part of the Assessment phase of ADAPT-ITT we will (1) administer an anonymous community-based survey adults 18 years and older on knowledge and perceptions about RSV and RSV vaccination for Aim 1 and (2) Conduct In depth Interviews (3) Community advisory board meetings using the ADAPT-ITT process to assess perceptions of RSV Vaccination and preferences for intervention components and knowledge and attitudes about RSV Vaccination. The ADAPT-ITT framework was designed to assist CBOs in adapting evidence-based interventions to fit new populations.

[figure not shown]
**Figure 2**

Summary of ADAPT-ITT Phases for Aim 1. The same process will be completed for Aim 1.1 & 1.2 individually

While our Unidos en Salud 'Motivate, Vaccinate, Activate' strategy is acceptable, feasible and effective for COIVD-19 vaccine uptake among Latinos, the core-components need adaptations for a different vaccine and infection (RSV), a non-pandemic setting, and different age-groups.

We will use the **Behavioral and Social Determinants (BeSD) of vaccination framework and core questions** for developing and coding our interview guides and to examine potential mediators of the effect of our interventions. The BeSD framework is informed by multiple theoretical models: COM-B, 3C's, socio-ecological model, and the Increasing Vaccination Model and identifies 2 domains, '*thinking and feeling*' and '*social processes*', as most associated with lack of vaccine confidence '*motivational conflict*', and a fourth domain '*practical issues*' as a domain that moderates the relationship between lack of vaccine confidence. In Figure 3 we present an adapted BeSD framework, which highlights intersections with our 'Motivate, Vaccinate, Activate intervention and highlights integration of the 3C's from the SAGE working group..

**Figure 3****Modified Behavioral and Social Drivers of Vaccination Mode (BeSD), 3Cs Model and intersections with trial interventions****4.2.2. Aim 1 Duration**

- Community-based survey on RSV Knowledge and Vaccine Confidence: Cross-sectional survey, which will last up to 25 minutes for 1 study visit.
- Community Advisory Boards Meetings for ADAPT-ITT: Community Advisory Board members will participate in 3-5 design sessions. The anticipated duration of involvement will be 12 months.
- In Depth Interviews: In-depth interviews on RSV vaccine confidence and preferences on text messaging and CHW counseling sessions for Aim 2 and 3. CAB members can participate in IDIs.

**4.2.3. Aim 1 Sample Size**

Aim 1 is a developmental Aim. Sample size is extrapolated for standard sample sizes needed for the ADAPT-ITT framework and to reach saturation for In Depth Interviews (IDIs).

**4.3. Study Design of Aim 2-Motivate Trial****4.3.1. Introduction and Rationale to Aim 2**

Drawing on our 'Motivate, Vaccinate, Activate' multi-component strategy and adaptations for RSV vaccination from Aim 1a, we will rigorously evaluate the effectiveness of a multi-component *CHW counseling session* and *CBO text-message intervention compared to text alone* (Figure 4). Our primary Hypothesis is that *text messages coupled with a community health worker counseling session will increase RSV vaccine uptake compared to text-message alone*. We hypothesize that the CHW counseling session will improve trust in the vaccine ability to navigate access-related barriers, and that this intent to vaccinate is reinforced by a text-message from a trusted source.

[figure not shown]
Understanding if there is an additional benefit to the more time-intensive CHW counseling will provide the evidence needed for CBOs and public health departments to design community-based RSV vaccination strategies for Latinos. We have chosen to not have a 'standard of care arm', but instead will compare the multi-component intervention to text-messages for three reasons: (1) Text-messaging interventions are low-cost intervention, which are effective in our

preliminary data (2) given the moderate anticipated effect size, power to detect benefit of adding text to the CHW intervention would require a sample size too large to be feasible given the intensity of the CHW intervention, and (3) we have modeled Arm 1 to mirror a 'lower intensity' CHW intervention akin to CHW outreach, with CHWs handing out an informational flyer at enrollment and receipt of a text message nudge.

#### 4.3.2. Study Population

CHWs and study staff will recruit from people accessing services or community fairs at LTF-affiliated CBOs in San Francisco. Study inclusion criteria include adults 50 and over who are eligible for the RSV Vaccine; detailed inclusion criteria are outlined in section 5.1.1.

**Figure 4: Schema of Aim 2 'Motivate Trial'**

#### 4.3.3. Study Design and Description of Intervention Groups

This is a two-arm randomized type-1 effectiveness-implementation individually randomized trial (Figure 4), with study groups:

**i) Arm 1- Text message nudge from CBO:** Participants will receive an educational flyer from a CHW about RSV vaccination and how to schedule it. Then 4 weeks after enrollment they will receive a text-message nudge, with message content based on findings in Aim 1a. This text message will also provide a flyer with vaccine information and eligibility. A phone number to the CHW team, the LTF hotline, for help with navigation will be provided on the flyer and in the text-message.

**ii) Arm 2: CHW counseling and text message nudge from a CBO:** At enrollment, participants will receive an educational flyer from a CHW, as in Arm 1, and will set up a time for the CHW counseling session. They can select remote (phone or web-based platform such as Zoom) or in-person counseling within 2 weeks of enrollment, and weekend hours will be offered. CHW counseling will consist of a 20-minute semi-scripted conversation grounded in the motivational interviewing principals of Five A's and adapted in Aim 1a. CHWs will assess participants beliefs and knowledge about RSV susceptibility and vaccine effectiveness, safety, and eligibility. They will advise and provide general information on vaccine eligibility and RSV susceptibility. Then, assist by assessing personal or structural barriers to vaccination and providing problem-solving techniques. Then arrange next steps: for navigation to a vaccine provider or interest in a follow-up call. CHWs will write down an action plan and give it to the participant, e.g. call clinic to make vaccine appointment in 5 days or follow-up call with CHW in 1 week. CHWs can provide general education about the vaccines: safety, eligibility, testimonials, but they will refer

individual medical questions to the participant's physician. CHWs will also provide a hotline for any questions or assistance with navigating health and vaccine linkage for participants.

#### 4.3.4. Location of interventions and survey procedures

The CHW counseling and baseline survey will be done via phone, Zoom or in person at the Mission Language Vocational School (Latino Task Force headquarters), ZSFG Clinical Research Center or in private locations in LTF-affiliated community venues. Endpoint follow-up can be done in-person in the same locations as the baseline visit or over the phone or Zoom, with survey completion done remotely using REDCap.

#### 4.3.5. Duration of study procedures

The duration of study procedures is 90 days, but participants can be in the study up to 24 months from enrollment if they are selected for in-depth interviews.

### 4.4. Study Design of Aim 3 – Activate Trial

#### 4.4.1. Introduction and Rationale:

The objective of Aim 3 is to determine the effectiveness of CHW 'activation' counseling and text-message nudges from a CBO on activating adults to discuss RSV vaccination with older adults in their social network.

[figure not shown]
In a parallel structure to Aim 2 we will conduct a randomized trial (Figure 5) of the intervention components (CHW counseling and text-message from a CBO) adapted in Aim 1.2.

Recommending vaccination not only requires confidence in the vaccine and knowledge about eligibility, but also capability and opportunity to initiate the conversation. We hypothesize that text messages coupled with a CHW

'activation' counseling session will increase the proportion of eligible people ( $\geq 50$  years) in with whom participants discuss RSV vaccination with, compared to text alone. Hypothesized mechanisms are that CHW counseling improves trust and knowledge of RSV vaccination and susceptibility, and the text-message nudges them to act on their intention to discuss RSV vaccine with family and people in their network.

**Rationale:** Interventions targeted to the social network have the potential to reach a large number of people with one contact point (i.e. the effect of CHW counseling with one person can be amplified to reach 5 of their social network contacts) and can impact social norms at the inter-personal or community level. Prior studies assessing the impact of interventions on participant's social network have been hampered by challenges documenting impact on social network contacts.

**Figure 5: Schema of Aim 3 'Activate Trial'**

To address this we will use 'name generation techniques' used in our prior studies to elicit the eligible contacts (adults  $\geq$ 50 years) of the 18-49 year old participants.

#### **4.4.2. Study Population**

CHWs and study staff will recruit from people accessing services or community fairs at LTF-affiliated CBOs or attending cultural events in San Francisco. Study inclusion criteria include Latino adults 18-49. Detailed inclusion criteria are outlined in section **5.1.1**.

#### **4.4.3. Study Design Aim 3 and Intervention Groups**

This is a two-arm type 1 effectiveness-implementation RCT randomized at the level of the individual (Figure 5) with the following **study groups**:

**Arm 1: Text message from a CBO:** Participants will receive an educational flyer from a CHW about RSV vaccination and how people in their network can schedule vaccines and the 'LTF hotline' for help with navigation if needed. Then 4 weeks later receive a text-message nudge, with message content based on findings in Aim 1b. As in Aim 2, the text message will also provide a flyer with vaccine information, eligibility, and scheduling from the LTF.

**Arm 2: CHW 'activation' counseling with text-message nudge:** At enrollment participants will receive the same flyer as in Group 1. Then, within 2 weeks of enrollment participants will have a 20-minute scripted conversation (in person or phone) grounded in motivational interviewing principals of Five A's. CHWs will assess participants beliefs and knowledge about RSV and vaccine effectiveness, safety, eligibility, *and* interest and barriers in recommending RSV vaccination to their friends or family. Then they will advise how to initiate conversations about RSV vaccination. CHWs will then assist, by assessing personal barriers to discussing vaccination with older adults. Then arrange next steps: CHWs will write down an action plan and give it to the participant. CHWs will also provide a hotline number for participants or their contacts to use for questions or support scheduling an appointment. Participants will receive a text-message nudge with scheduling and information 1 month after enrollment.

#### **4.4.4. Location of CHW interventions and survey procedures**

The CHW counseling and baseline survey will be done via Zoom or in person at either Mission Language Vocational School (Latino Task Force headquarters), ZSFG Clinical Research Center. Endpoint follow up can be done in-person or remotely over Zoom or the phone.

#### **4.4.5. Duration of study intervention**

The intervention will be received at baseline (CHW counseling) and the text will be received 4 weeks after follow-up. The duration of study procedures is 90 days, but participants can be in the study up to 24 months from enrollment if they are selected for in depth interviews.

#### **4.5. Primary Completion**

The expected completion of the primary outcome of Aim 2 and 3 is 4 years after the study opens to accrual.

#### **4.6. Study Completion**

The expected study completion date is 5 years after the study opens to accrual.

## 5. Selection and Enrollment of Participants

### 5.1. Eligibility Criteria

#### 5.1.1. Inclusion Criteria and Exclusion Criteria

Inclusion and Exclusion criteria for all three aims are outlined in Table 4.

**Table 4: Inclusion and Exclusion Criteria**

Study	Inclusion Criteria	Exclusion Criteria
Aim 1		
RSV Vaccine Confidence Survey	(a) Adult age $\geq 18$ years (b) Speaks Spanish or English	Not able to provide informed consent
Community Advisory Groups for Adaptation of Intervention	1. Group 1: a. age $\geq 60$ years b. speaks Spanish or English c. self-identifies as Latino/a/e/x and/or indigenous group from Latin America d. lives or works in San Francisco County or Daly City and able to come to in-person meetings in San Francisco 2. Group 2: a. age 18-50 b. speaks Spanish or English c. Self-identifies as Latino/a/e/x and/or indigenous group from Latin America d. lives or works in San Francisco or Daly City and able to come to in-person meetings in San Francisco	Not able to provide informed consent  Planning on moving out of San Francisco or Daly City area in 12 months
In Depth Interviews (Aim 1)	(a) Self-identifies as Latino/a/e/x and/or indigenous group from Latin America (b) Speaks Spanish or English (c) Age $\geq 18$ years	Not able to provide informed consent
Aim 2 'Motivate Trial'	Inclusion Criteria: (a) Age $\geq 50$ years (b) Self-identify as Latino/a/x and/or indigenous groups from Latin America	(a) Intent to move outside of San Francisco in the next year

	
 
(c) Eligible for RSV vaccination per current CDC/ACIP recommendations*
 
(c) Fluent in Spanish or English
 
(d) Has not received the RSV vaccine
 
(e) Has a cell phone
 
(f) Lives or works in San Francisco or Daly City
 
(f) Able to provide informed consent
 
 
* CDC/ACIP Eligibility for RSV Vaccination:
 
 
(1) Age 75 years and older
 
(2) Age 50-74 and one of the following medical comorbidities: cardiovascular disease (e.g. coronary artery disease), lung disease (e.g. COPD, asthma), advanced chronic kidney disease, diabetes, liver disorders, neurologic or neuromuscular conditions, hematologic disorders, moderate or severe immune compromise
 
	
 
(b) Nursing home resident
 
(c) Household member participating in Aim 1 or 2
 
(d) Unable to provide consent
 

Aim 3 'Activate Trial'	
Inclusion Criteria:
 
 
(a) Age 18-49 years
 
(b) Self-identify as Latino/a/x and/or indigenous groups from Latin America
 
(c) Fluent in English or Spanish
 
(e) Has a cell phone
 
(f) Has <math>\geq 1</math> family member or friend 50 years or older who they have seen or spoken to for <math>\geq 15</math> minutes in the last 6 months and who lives in the United States
 
	
Exclusion Criteria:
 
 
(a) Household member enrolled in Aim 1 or 2
 
(b) Unable to provide consent
 

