## 5.2. Recruitment Methods for Aims 1-3

### 5.2.1. Recruitment

Bilingual study staff in partnership with community health workers will recruit eligible participants among people who are receiving services or attending community cultural or health fairs at Latino Task Force (LTF) community sites, CBOs affiliated with the Latino Task Force, or other events in the community. Study team will present the study to Latino Task Force community

meetings. Staff and community health workers will distribute IRB-approved flyers about the study at community-events and answer questions about the study. While CHWs will participate in outreach, enrollment will be done by UCSF study staff. Information about the study will be shared at Latino Task Force meetings and affiliated CBOs will receive recruitment flyers, that they can also post and share with client. If a client expresses interest in the study, the study staff will follow-up with the client to discuss the study further, screen for eligibility, and set a date for the baseline visit if the individual is interested in participating.

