### **6.3. Participant Discontinuation/Withdrawal from the Study**

Participants are free to withdraw from participation in the study at any time upon request.

An investigator may discontinue a participant from the study for the following reasons:

- Unacceptable adverse event(s)
- Significant study intervention non-compliance.
- Lost-to-follow up; unable to contact participant (see Section 6.4 - Lost to Follow-Up)
- Any event or medical condition or situation occurs such that continued collection of follow-up study data would not be in the best interest of the participant .
- The participant meets an exclusion criterion (either newly developed or not previously recognized) that precludes further study participation

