## 9. Statistical Considerations

This study includes a developmental aim (Aim 1) to adapt interventions tested in Aim 2 and 3. Herein we present the statistical design and power for randomized trials in Aim 2 and 3.

In Aim 2, we will compare the effectiveness of two strategies—Arm 1: RSV vaccine information flyer at enrollment + text-message nudges vs. Arm 2: Community Health Worker (CHW) counseling *and* text message nudges—on RSV vaccine uptake among 400 Latino adults  $\geq$  50 years. In Aim 3, we will compare the effectiveness of two strategies: Arm 1: RSV vaccine information flyer at enrollment + text-message nudges vs. Arm 2: Community Health Worker (CHW) 'activation' counseling *and* text message nudges—on enabling participants (18-49 years old) to discuss RSV vaccination with older adults in their family and social network. We will conduct in-depth qualitative interviews with a subset of participants from Aim 2 and 3, with stratified sampling based on key outcome measures. We will also describe implementation outcomes for text-messaging and CHW counseling, using metrics that align with the RE-AIM framework.

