### **9.3. Aim 3 (Activate Trial) Analysis Plan**

**Aim 3 Study Design:** Two-arm randomized type-1 effectiveness-implementation individually randomized trial.

**Aim 3 Analysis Plan:** We will take an analogous analytic approach to Aim 2 to evaluate our primary outcome, 'the average proportion of older adult contacts with whom RSV vaccination was discussed' between the two study arms' and secondary outcomes, together with pre-specified subgroup analyses (age group 18-29 vs. 30-49 years). We will also undertake additional social network analyses to assess the relationship between egocentric network characteristics and the odds of discussing RSV vaccination: network size, type of relationship (e.g grandmother vs. aunt), characteristics of the participant (e.g. lives in multigenerational household, vaccine confident, age, acculturation), by study arm and pooled across arms.

**Implementation Outcomes:** We will use definitions outlined in Table 2 and analogous quantitative and qualitative methods outlined in Aim 2.

In a nested secondary pre-post analysis we will compare the proportion of people who discussed the RSV vaccine with eligible family or friends prior to the text-message to 30 days after the text.

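### The Motivate household exclusion leaves out Aim 3, so a mixed Motivate/Activate household is refused or admitted according to who enrolls first (minor)

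*Protocol*

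**What the plan says.** Protocol Section 5.1.1, Table 4, sets a household rule for each trial.

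- Motivate (Aim 2, age 50 and over), exclusion (c): "Household member participating in Aim 1 or 2".
- Activate (Aim 3, age 18-49), exclusion (a): "Household member enrolled in Aim 1 or 2".

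Both lists name Aims 1 and 2. Neither names Aim 3.

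Section 9 gives the purpose of Activate as "enabling participants (18-49 years old) to discuss RSV vaccination with older adults in their family and social network". For Arm 2, the community health worker (CHW) session in Section 4.4.3 includes this step: "Then they will advise how to initiate conversations about RSV vaccination". Section 9.3 lists "lives in multigenerational household" among the participant characteristics to be analyzed in Activate. Recruitment for all aims draws on people "receiving services or attending community cultural or health fairs at Latino Task Force (LTF) community sites" (Section 5.2.1), affiliated organizations and other community events. On timing, Section 4.5 says: "The expected completion of the primary outcome of Aim 2 and 3 is 4 years after the study opens to accrual".

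**The concern.** A household exclusion across trials protects only if it works in both directions. Here it works in one. The age ranges adjoin, the recruitment sites are shared, and the analysis plan itself allows for Activate participants in multigenerational homes, so a mixed pair is realistic.

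Two spillover routes follow when the follow-ups overlap:

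- **Into Motivate.** An Activate participant, especially one in Arm 2, may raise RSV vaccination with the older co-resident. If that prompt does part of the work of CHW counseling, the contrast between counseling plus text and text alone shrinks.
- **Into Activate.** The primary outcome is the proportion of contacts named at baseline with whom vaccination was discussed. The sample questions (Figure 7) ask whether a discussion took place. They do not ask who began it. A named co-resident who is surveyed, texted or counseled in Motivate may open the conversation, and it then counts in either Activate arm.

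The sample-size sections (9.2.1 and 9.3.1) allow for counseling reach or loss to follow-up, but not for spillover between the trials.

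**Working it through.** **1. Order check.** Applying the two Table 4 exclusions to the second person in a household:

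| First to enroll | Second to apply | Rule applied to the second person | Result |
|---|---|---|---|
| Motivate | Activate | Aim 3 exclusion (a) names Aim 2 | excluded |
| Activate | Motivate | Aim 2 exclusion (c) does not name Aim 3 | admitted |
| Motivate | Motivate | Aim 2 exclusion (c) names Aim 2 | excluded |
| Activate | Activate | Aim 3 exclusion (a) does not name Aim 3 | admitted |

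Rows 1 and 2 are the same household with opposite results. Row 4 is a separate matter and is not part of this point.

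**2. Is the gap closed elsewhere?** The nearest text is Section 6.3, which lets an investigator discontinue someone when "The participant meets an exclusion criterion (either newly developed or not previously recognized) that precludes further study participation". It could reach the Activate member once the relative joins Motivate. But it is discretionary, it acts after entry, and it does not bar the older adult from Motivate.

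**3. Size in Activate.** There is no Protocol figure to reproduce, because the share of mixed households is not given. The following is an illustration.

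- From Section 9.3.1: expected proportions of 30% and 40%, a difference of 10 points.
- Assumed: 3 named contacts per participant; one is a Motivate co-resident who always has the discussion, whatever the Activate arm; 5-10% of Activate participants are affected.

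Affected participants:

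- Arm 1: (0.3 × 2 + 1)/3 = 0.533
- Arm 2: (0.4 × 2 + 1)/3 = 0.600
- Difference: 0.067 instead of 0.100, a loss of 0.033

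Whole trial: 0.033 × 5% = 0.17 points and 0.033 × 10% = 0.33 points, so about 0.2-0.3 of 10 points.

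**4. Size in Motivate.** Section 9.2.1 expects 28% in the text arm and takes 10 points as the minimum detectable difference, hence 28% and 38%. Because Motivate randomizes individuals, a share *s* exposed at home to an Activate Arm 2 participant is expected equally in both arms.

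- If the prompt adds the same number of points, *a*, in both arms: (0.38 + *sa*) − (0.28 + *sa*) = 0.10. Nothing is lost.
- If the prompt vaccinates a fraction *q* of those otherwise unvaccinated, each arm's uptake *p* becomes *p* + *sq*(1 − *p*). The difference becomes 0.10 × (1 − *sq*), a loss of 10 × *q* × *s* points.

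Assume *q* = 20% and *s* = 2.5-5% (half of 5-10%, since half of Activate is in Arm 2). The loss is 10 × 0.20 × 0.025 = 0.05 to 10 × 0.20 × 0.05 = 0.10 points. Even at *q* = 100% it would be 10 × 0.025 = 0.25 to 10 × 0.05 = 0.5 points.

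**The case against.** The strongest case is that the asymmetry is real but its consequences are slight and partly unproven. Most of that stands.

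- **Overlap is not established.** A joint completion date does not show that the trials enroll at the same time, and the timeline figures are not available. Activate follow-up that ended at 60 days, before the relative joined Motivate, cannot be affected. A relative already vaccinated through Activate is ineligible for Motivate. A reader might infer that every mixed pair contaminates both trials; the Protocol does not support that. Nor does it rule overlap out: no text places Motivate before Activate.
- **No lost hotline contrast.** A reader might infer that a text-only Motivate participant would gain CHW scheduling help that the arm should lack. Section 4.3.3 already gives Arm 1 the hotline number for navigation, on the flyer and in the text message. What remains is a conversation with a relative, which is not the 20-minute counseling session.
- **No bias toward one arm.** It is tempting to count home exposure in Motivate Arm 1 only. Independent randomization makes it equally likely in both arms, so the difference narrows only where prompt and counseling overlap.
- **The Activate illustration is extreme.** Motivate counseling concerns the participant's own beliefs, barriers and navigation. Nothing suggests that the co-resident would always start the discussion.
- **Intent is inferred.** The Protocol nowhere explains why the household rules exist.
- **The remedy is partial.** Activate contacts may be any family member or friend aged 50 or over in the United States. Those living elsewhere stay eligible for Motivate.

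None of this removes the inconsistency: who enrolls first is not a sensible basis for admitting a household.

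**Conclusion.** The point holds as a minor eligibility inconsistency. Table 4 refuses or admits the same Motivate/Activate household by order of enrollment, and no other text in the Protocol closes the gap.

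The expected consequence, where follow-up overlaps, is a small dilution of the arm contrasts. Its size cannot be computed from the Protocol. The illustration for Activate (about 0.2-0.3 of 10 points) rests on an assumed 5-10% of participants affected, three contacts each, and a co-resident who always discusses; it is closer to a ceiling for that share than to an expectation. For Motivate the loss is zero if the home prompt adds equally in both arms, and about 0.05-0.10 points under the assumed partial redundancy. The reason to act is that the rule is inconsistent and cheap to repair, not that either trial's result is threatened.

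**What to change.** Add Aim 3 to the aims named in Motivate exclusion (c), so that a household member in Aim 1, 2 or 3 excludes, and add the matching question to the Motivate screening form. The Activate-then-Motivate order then changes from admitted to excluded, and both orders of a mixed pair are treated alike.

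The cost is one amended criterion, one screening question and a few otherwise eligible older adults lost to Motivate. No sample-size or power figure changes. The amendment acts only on future enrollment, so mixed pairs already admitted stay exposed. It also leaves open spillover through contacts who live outside the household.
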